4 INTRODUCTION

4.1 *Background Information*

Globally, an estimated 360 million people are chronically infected with hepatitis B virus (HBV) and up to 1 million a year die because of hepatocellular carcinoma, cirrhosis of the liver, or liver failure caused by HBV. When drug treatment is deemed appropriate, the current treatment for chronic HBV infection is a daily oral dose of nucleotide/nucleoside analogs (NUC) (depending on renal function) or a regimen of interferon injections 1 to 7 times weekly for a year or longer. Nucleotide/nucleoside analogs effectively reduce viral deoxyribonucleic acid (DNA) production by inhibiting the viral polymerase, but patients can expect to take these antivirals for life because viral replication quickly rebounds upon cessation of treatment in more than half of patients who are HBeAg (+) at baseline and more than 80% in patients who are HBeAg (-) with Chronic Hepatitis B (CHB). A more desirable outcome would be HBV surface antigen (HBsAg) loss with or without S-antigen seroconversion, which is an effective antibody response to the envelope protein that is also called HBsAg. S-antigen loss (with or without seroconversion to Anti-HBsAg) represents immune mediated viral clearance and is considered a functional cure, if HBV DNA is also undetectable. Nucleotide/nucleoside analog treatment has very little effect, if any on the level of HBsAg that is produced, nor on production of the other viral proteins. The highly abundant HBsAg produced in the infected patient, as high as 10^{12} particles/mL of blood, is believed to counteract virus-neutralizing Anti-HBsAg antibodies, allowing the virus to spread cell to cell and to be maintained in the host. The large quantities of secreted HBsAg also lead to T-cell exhaustion and anergy. Thus, even on NUC therapy, the rate of HBsAg loss in CHB patients is only about 1% annually, even after many years of NUC treatment. The rate of HBsAg clearance is similarly low from interferon treatment, and these therapeutics cause significant side effects, including severe flu-like symptoms, bone marrow suppression, and autoimmune disorders. The lack of satisfactory therapeutics for treatment of chronic HBV infection highlights the need for a different approach to this disease.

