CHB patients regardless of HBeAg status or NUC/Interferon use history will enroll sequentially in Cohorts 2b through 7, Cohorts 10 and 11, and Cohorts 1b and 1c into a total of 10 open label cohorts. Cohorts 1b, and 1c through 5b will enroll at planned dose levels of 25 mg (Cohort 1b), 50 mg (Cohort 1c), 100 mg (Cohort 2b), 200 mg (Cohort 3b), 300 mg (Cohort 4b) and 400 mg (Cohort 5b) to receive three doses (Q28 days) of active treatment in an open label fashion. Cohorts 6 through 12 will enroll at planned dose levels of 100 mg (Cohorts 6 and 7), 200 mg (Cohort 10, 12), and 300 mg (Cohorts 8, 9, and 11). Cohort 6 will enroll CHB subjects (after Cohort 5b has completed enrollment) to receive three doses two weeks apart. Cohorts 7, 10 and 11 will enroll CHB patients sequentially (after Cohort 6 has completed enrollment) to receive three doses a week apart at increasing dose levels starting with a dose equal to Cohort 6. Cohorts 5b through 7 and Cohorts 10 and 11 will enroll sequentially (after being opened at the final planned DSC meeting) with enrollment and dosing in a later cohort not initiating until all subjects in the earlier cohort have received at least their first scheduled dose. Cohort 8 will enroll HBeAg positive treatment naïve CHB patients to receive three monthly doses of ARO-HBV. Cohort 9 will enroll HBeAg positive entecavir or tenofovir experienced CHB patients to receive three monthly doses of ARO-HBV. CHB patient screening for all CHB cohorts may start when Cohort 1 opens for enrollment. However, no CHB patients may be dosed until their respective cohort is approved for dosing by the DSC (not including Cohorts 1b,1c and 12). CHB dosing may begin and NHV dose escalation may occur based on DSC approval which can occur by vote after cumulative data through Day 8 from the current NHV cohort is available. (See **Figure 1** for dose escalation schedule).

CHB patients on current NUC therapy (entecavir or tenofovir) will stay on NUC therapy for the study duration. CHB patients not on NUC therapy (NUC naïve) will be started on either entecavir or tenofovir (selection between entecavir and tenofovir based on site Principal Investigator (PI) discretion) on Day 1. Either tenofovir disoproxil fumarate (including generic) or tenofovir alafenamide are acceptable. During the extended follow up period after Day 113, NUCs may be discontinued at investigator discretion if subject becomes HBsAg undetectable (< 0.05 IU/mL).

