For clarity, after Cohort 5 is through Day 8, the DSC will review all available safety data and vote to open Cohorts 5b, 6, 7, 8, 9, 10 and 11. Cohorts 5b, 8 and 9 may enroll and dose patients in parallel. Cohorts 5b through 7 and Cohorts 10 and 11 must enroll sequentially, meaning that Cohort 5b must be fully enrolled with each subject receiving at least a first dose before Cohort 6 can enroll. Cohort 6 must be fully enrolled with each subject receiving at least a first dose before Cohort 7 can enroll. Cohort 7 must be fully enrolled with each subject receiving at least a first dose before Cohort 10 can

enroll and Cohort 10 must be fully enrolled with each subject receiving at least a first dose before Cohort 11 can enroll. It is the intent that Cohorts 7, 10 and 11 will be treated at increasing dose levels starting with a dose equal to Cohort 6.

[figure not shown]
[figure not shown]
[figure not shown]

[figure not shown]

[figure not shown]
[figure not shown]
On dosing days, clinical facility confinement will be approximately 2 hours unless a longer period of post-dose observation is needed based on PI discretion. Blood samples will be drawn pre-dose on Day 1 for baseline measurements. Height and weight will be measured at Screening only to calculate BMI. Participants will undergo evaluations at screening and at regular intervals during the study as described in the Schedule of Assessments.

With the exception of Cohort 12 patients, all other CHB patients consenting to additional follow up will be followed as per Additional Follow-Up Schedule of Assessments (Table 1.5), every 56 days (\pm 5 days) for 5 additional visits after Day 113. Only Cohort 12 patients will require follow-up until the Day 337 (\pm 5 days) visit. Subjects consenting to additional follow up will continue on NUCs and may have NUCs discontinued at the investigator’s discretion if patients become HBsAg undetectable ($<$ 0.05 IU/mL). Subjects not consenting to additional follow up will be followed per protocol based on Schedule of Assessment Tables 1.2, 1.3 and 1.4.

Single doses of ARO-HBV will be evaluated in normal healthy volunteers (NHVs) and multiple doses of ARO-HBV will be evaluated in patients with chronic hepatitis B (CHB) in a sequential manner as shown in **Figure 1**.

Figure 1. Dose Escalation Schedule

Healthy Volunteers (double blind)*			CHB Patients (open label)	
Cohort	Dose (Day 1)	Day 8 safety evaluation	Cohort	Dose Regimen

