For each CHB patient in the multi-dose cohorts the duration of the study clinic visits is approximately 25 weeks from screening to the Day 113 EOS examination. With the exception of Cohort 12 patients, all other CHB patients consenting to additional follow up will be followed as per Additional Follow-Up Schedule of Assessments (Table 1.5), every 56 days (± 5 days) for 5 additional visits after Day 113. Only Cohort 12 patients will require follow-up until the Day 337 (± 5 days) visit. Subjects consenting to additional follow up will continue on NUCs. Subjects not consenting to additional follow up will be followed per protocol based on Schedule of Assessment Tables 1.2, 1.3 and 1.4.

All CHB subjects who complete the study until Day 113 EOS examination are considered to complete the study and may continue to attend the Additional Follow-Up visits per the Schedule of Assessments (Table 1.5) if re-consent is obtained. If a subject withdraws from the Additional Follow-Up visits before the Day 337 (Cohort 12 only) or 393 visit, he or she will still be considered as a completed subject and reason for not continuing with the Additional Follow-Up visits per protocol will be recorded.

All CHB patients and NHV subjects will be contacted by phone 90 days after the EOS visit (Day 29 for NHVs and Day 113 for CHB patients) to confirm pregnancy status.

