- 3. *Recreational Drugs & Alcohol:*** Participants will be instructed to abstain from consuming alcohol for at least 48 hours prior to admission, and whilst confined to the clinical facility. In addition, participants will be instructed to refrain from regular use of alcohol (i.e., more than fourteen units of alcohol per week [1 Unit = 150 mL of wine, 360 mL of beer, or 45 mL of 40% alcohol]) for the study duration. Participants should abstain from use of recreational drugs throughout the study.
- 4. *Concomitant Medications Healthy Volunteers:*** Subjects will be instructed not to take any prescription medication (other than medications used as part of the study) for 7 days prior to admission and for the duration of the study. Oral or other hormonal contraceptives are acceptable. Subjects will be instructed to inform the PI of the details (indication, dose and dates of administration) if they do take any medication, and these details will be recorded in the CRF. If necessary, paracetamol may be used during the study as necessary. Any other medication or therapy other than blood pressure medication must be approved by the Medical Monitor or PI prior to administration.

5. **Concomitant Medications CHB Patients:** Use of concomitant medications during the study is at the discretion of the PI unless otherwise specified. However, participants should not be on medications that would interfere with study evaluations. Topical or inhaled steroids, statins, hypertensive medications, and birth control (where appropriate), and oral analgesics are acceptable. Participants will be instructed not to take any anticoagulants (aspirin and antiplatelet agents are acceptable), systemic (oral, depo or intramuscular) corticosteroids, immunomodulators (other than those specified in the study), or immunosuppressants 14 days prior to dosing and for the duration of the study. Participants will be instructed to inform the PI of the details (indication, dose, and dates of administration) if they do take any medication, and these details will be recorded in the eCRF. CHB patients entering the study on entecavir or tenofovir will continue their NUC therapy at the prescribed dose and frequency throughout the study. All treatment naïve CHB patients entering the study will start on entecavir or tenofovir on Day 1.

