CHB cohorts 1b, 1c, 2b, 3b, 4b and 5b will each enroll a minimum of 4 and a maximum of 8 subjects and the remaining CHB cohorts (except Cohort 12) will each recruit a maximum of 4 chronic hepatitis B patients, with all subjects receiving three doses of ARO-HBV at dose intervals ranging from once every week to once every 4 weeks in an open label fashion. All CHB cohorts except Cohorts 8 and 9 will include CHB patients regardless of NUC or HBeAg status. Cohort 8 will include HBeAg(+) and treatment naïve patients, and Cohort 9 will include HBeAg(+) and entecavir or tenofovir experienced patients. CHB patients on current nucleos(t)ide (NUC) therapy (entecavir or tenofovir) will stay on NUC therapy for the study duration. CHB patients not on NUC therapy (NUC naïve) will be started on either entecavir or tenofovir (selection between entecavir and tenofovir based on site Principal Investigator (PI) discretion) on Day 1. Cohort 12 will enroll 12 CHB patients who will either enter the study on NUCs or start NUCs on Day 1. Cohort 12 patients will also initiate daily JNJ-56136379 (JNJ-6379) 250 mg on Day 1 and continue through Day 84.

CHB cohorts will be multi-dosed as follows:

- Cohort 1b: 25 mg ARO-HBV, at Days 1, 29 and 57
- Cohort 1c: 50 mg ARO-HBV, at Days 1, 29 and 57
- Cohort 2b: 100 mg ARO-HBV, at Days 1, 29 and 57

- Cohort 3b: 200 mg ARO-HBV, at Days 1, 29 and 57
- Cohort 4b: 300 mg ARO-HBV, at Days 1, 29 and 57
- Cohort 5b: 400 mg ARO-HBV, at Days 1, 29 and 57
- Cohort 6: 100 mg ARO-HBV, at Days 1, 15 and 29
- Cohort 7: 100 mg ARO-HBV, at Days 1, 8 and 15
- Cohort 8 (HBeAg +, Treatment naïve): 300 mg ARO-HBV, at Days 1, 29 and 57
- Cohort 9 (HBeAg +, NUC (entecavir/tenofovir) experienced): 300 mg ARO-HBV, at Days 1, 29 and 57
- Cohort 10: 200 mg ARO-HBV, at Days 1, 8 and 15
- Cohort 11: 300 mg ARO-HBV, at Days 1, 8 and 15
- Cohort 12: 200 mg ARO-HBV, at Days 1, 29 and 57 + 250 mg daily JNJ-6379 + NUCs

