### Time to Event Endpoints

- Time to HBsAg Loss is defined as the duration from first dosing to the date of HBsAg 'Not Detected' (HBsAg loss defined as HBsAg < 0.05 IU/mL). Subjects without HBsAg loss will be censored at the end of study (or the end of follow-up period).
- Time to anti-HBsAg seroconversion is defined as the duration from first dosing to the date of anti-HBsAg seroconversion. Subjects without anti-HBsAg seroconversion will be censored at the end of study (or the end of follow-up period).
- Duration of Response (for HBV DNA, qHBsAg, qHBeAg, qHBcrAg, qHBV RNA): defined as the duration from post dose nadir back to within 20% of baseline value. The analysis will only be performed for the overall study period (including the follow-up period) and only patients with baseline values above the LLQ for the specific parameter will be included in the analysis. Subjects with the endpoint not returning to within 20% of baseline value will be censored at the end of the follow-up period.

The time to event endpoints will be analyzed by survival analysis method. Survival analysis will only be conducted if there are at least some responders within a cohort. The survival functions of the time to event endpoints will be summarized for 25th percentile, median, and 75th percentile and their 95% confidence intervals. The rates of HBsAg Loss and anti-HBsAg seroconversion at Day 60 and Day 113 post dosing (and also at Days 169, 225, 281, 337 and 393 for the subset of CHB subjects that participated in the follow-up), the response rates (for HBV DNA, qHBsAg, qHBeAg, qHBcrAg, qHBV RNA) at Day 30 and Day 60 (and additional time points at 30 days intervals as appropriate) post nadir, and their respective 95% confidence intervals will be derived based on their survival functions estimated by Kaplan-Meier method. In addition, the graphs of Kaplan-Meier estimates of survival functions (survival plots) will be presented. Histograms will also be presented showing the response rates for each cohort over 30-day intervals.

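### Protocol 6.1 allows NUCs to be stopped in follow-up after HBsAg loss, other sections on the same period do not, and the SAP cannot tell an HBV DNA rebound off NUCs from one on NUCs

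*Protocol*

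**What the plan says.** Protocol 6.1 gives the permission twice. Its paragraph on NUC therapy ends: "During the extended follow up period after Day 113, NUCs may be discontinued at investigator discretion if subject becomes HBsAg undetectable" (below 0.05 IU/mL). Its paragraph on additional follow-up says: "Subjects consenting to additional follow up will continue on NUCs and may have NUCs discontinued", on the same HBsAg condition and again at the investigator's choice.

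The other follow-up statements carry no exception. The synopsis (under Study Duration and again under Study Design/Methods), Section 6.4, Section 9.1 and Section 9.3.9 all say: "Subjects consenting to additional follow up will continue on NUCs". Section 7.5 says that patients who enter on entecavir or tenofovir "will continue their NUC therapy at the prescribed dose and frequency throughout the study".

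SAP 2.1 says that patients already on NUCs "will stay on NUC therapy for the study duration", and SAP 2.5 has every CHB patient receiving daily NUC. The SAP is written against Protocol Version 6.0, which contains the permission, but it does not mention NUC discontinuation. Its duration-of-response endpoint, for HBV DNA, HBV RNA and three antigens, is "defined as the duration from post dose nadir back to within 20% of baseline value". It is analysed over the whole study including follow-up, and the only censoring is at the end of follow-up. NUC data are listed (SAP 8 and 10.2) but enter no virology analysis.

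**The concern.** Two sites with the same patient, HBsAg undetectable after Day 113, could act differently according to which section they consult. Section 9.3.9 is the follow-up procedures section, and a site working from it could record as a deviation what 6.1 allows. SAP 4 decides subject by subject whether patients with protocol violations stay in the PD population, so the ambiguity could also affect who is analysed.

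The point bears on safety. Section 4.7.1 names NUC discontinuation as a setting for HBV DNA rebound and ALT elevation, and its mitigation of flare risk relies on patients starting NUCs or being kept on them.

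For the analysis, an HBV DNA rise after NUCs are withdrawn has a different meaning from a rise on NUCs. The SAP would put both in one curve and one set of visit summaries. The patients concerned are those who have lost HBsAg, whose later course will be read most closely.

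**Working it through.** The plan gives no figure on this point, so the check is a comparison of texts followed by a small illustration.

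**1. Which statements govern the period after Day 113?**
- Stopping allowed, conditionally: Protocol 6.1, two places.
- Continue, explicitly in additional follow-up, no exception: the synopsis (two places), 6.4, 9.1 and 9.3.9, five places in all.
- Continue, worded by study length: the synopsis (Study Population), 6.1, 7.5 and SAP 2.1. Section 6.4 treats a patient who reaches Day 113 as having completed the study, so these can be read as ending there. That reading does not reach the five explicit follow-up statements.

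**2. What does the SAP do with an HBV DNA rebound after NUC stop?** A return to within 20% of baseline is an event whatever the NUC status. Nothing censors or marks the stop. For patients below the quantitation limit at baseline, SAP 11 excludes the parameter from duration of response. If they later exceed the limit they appear in a separate listing of patients who worsened, again without a NUC-stop marker.

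**3. Who can be affected?** A patient must have baseline HBV DNA at or above the limit (20 IU/mL), have HBsAg below 0.05 IU/mL in follow-up, stop NUCs, and rebound far enough. The SAP does not say whether the 20% applies to the raw or the log10 value. For an illustrative baseline of 7 log10 IU/mL:
- raw scale: 7 + log10(0.8) = 6.90, a return to within 0.10 log;
- log10 scale: 0.8 × 7 = 5.60, a return to within 1.40 log.

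A smaller rebound is not an event.

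**4. How many could be eligible to stop?** The planned CHB total is 60 to 84 (SAP 2.4). The documents give no expected rate of HBsAg loss on ARO-HBV. Section 4.1 gives about 1% a year on NUCs; 5% and 10% are assumptions. Patients eligible = N × rate:
- 1%: 0.6 to 0.84
- 5%: 3 to 4.2
- 10%: 6 to 8.4

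These assume that everyone enters follow-up. Those who stop, have quantifiable baseline DNA and rebound will be fewer.

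**5. What does one case do?** With n patients analysed, all at risk and the others still in response, one event takes the Kaplan-Meier estimate from 1 to 1 − 1/n. Censoring that patient at NUC stop leaves it at 1.000.
- n = 4: 1 − 1/4 = 0.750, a drop of 25 points
- n = 8: 1 − 1/8 = 0.875, a drop of 12.5 points
- n = 12: 1 − 1/12 = 0.917, a drop of 8.3 points

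The values 4, 8 and 12 are the planned cohort sizes in Protocol 6.1. The number analysed may be smaller, which makes the step larger.

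**The case against.** The best reply is that 6.1 states a default and then a narrower exception, which is ordinary drafting, and that the other sections merely lack a clause. This stands for 6.1 read alone. It does not settle the matter for a site that relies on 9.3.9, 6.4 or the synopsis, where nothing points to an exception.

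The stakes are also limited. The study is descriptive. The primary objective (related adverse events) and the secondary virology objective (HBsAg reduction to nadir) do not depend on this rule, HBV DNA and RNA are exploratory, and individual curves and NUC listings will be available. All of that stands.

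A reader might infer more than the documents support:
- *That most patients who stop will rebound.* Section 4.1 says that "viral replication quickly rebounds upon cessation of treatment in more than half of patients who are HBeAg (+) at baseline", and more than 80% of HBeAg-negative patients. Those rates describe NUC cessation in general, not after HBsAg loss. The same section links seroclearance to lasting absence of viremia off therapy, and 4.6 foresees that functional cure may let patients stop antivirals. No rebound rate is given for the patients at issue.
- *That HBV RNA rebounds too.* No section says so. The same SAP rule would merely count it if it did.
- *That nadir results are biased.* The nadir is the largest post-dose decline, so a later rise cannot worsen it.
- *That post-stop values should be removed.* Stopping is conditional on HBsAg loss, so censoring there may be informative, and removal would hide HBV DNA off therapy, where durability would be seen. An all-data analysis is legitimate.

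**Conclusion.** The conflict in the current protocol text is real and should be resolved, because it concerns continuing antiviral therapy and the protocol itself ties stopping to viral rebound and ALT elevation. Which rule is right is not a matter for this review.

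The SAP gap is real but smaller. If stopping remains possible, an HBV DNA rebound off NUCs counts as the end of response and cannot be told from a rebound on NUCs. Visit-by-visit follow-up summaries of HBV DNA mix the two in the same way. The number of patients is probably small and cannot be predicted from the documents. The 25, 12.5 or 8.3 point step per case rests on 4, 8 or 12 patients being analysed, all at risk and the others in response, and on a rebound that meets the 20% criterion. The main antigen, HBsAg, is less exposed, since Section 4.1 says that NUCs have little if any effect on it.

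**What to change.** **Protocol.** Reconcile the synopsis and Sections 6.1, 6.4, 7.5, 9.1 and 9.3.9 so that one NUC rule applies after Day 113, and bring SAP 2.1 and 2.5 into line. The sponsor and investigators decide the rule.

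**SAP 11, if stopping remains possible.**
- Derive a NUC stop date from records already collected. Medication dates go into the eCRF (Protocol 7.5), and concomitant medications are recorded at every follow-up visit (Table 1.5).
- Flag HBV DNA and HBV RNA values after that date in the follow-up tables, figures and listings, including the listing of patients below the limit at baseline who later exceed it.
- Keep the all-data duration-of-response analysis for HBV DNA and HBV RNA, and add a sensitivity analysis censored at NUC stop.
- State whether the 20% criterion applies to raw or log10 values.

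**Cost.** Wording changes and a little programming, with no new data. Because the censoring may be informative, the censored analysis supplements the main one and does not replace it.

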6.2 Rationale for Study Design

This first-in-human study plans to investigate ARO-HBV in adult healthy volunteers (NHVs) and HBV patients to evaluate the drug's safety and tolerability as well as its pharmacokinetics in healthy volunteers and pharmacodynamics in HBV patients, following a single (or multiple subcutaneous doses in HBV patients). The study initiates in NHVs because the single dose risk is considered low. Additionally, this population will be otherwise healthy without co-morbidities that may increase risk

for toxicity. The siRNA triggers in ARO-HBV are targeted against the mRNA transcripts generated by HBV viral cccDNA and integrated DNA. Since NHVs will not have HBV infection the potential for toxicity due to pharmacodynamic (e.g. “on-target”) effect is very low. After a period of post-dose safety evaluation in NHVs at each dose level, multi-dose (3 dose) cohorts in HBV patients at the same dose levels are planned (See Figure 1). Multiple doses of ARO-HBV are employed in the HBV patient cohorts as it is highly likely that prolonged reduction of viral antigens will be required to elicit functional cures. It is also important to note that this study excludes patients with excessive co-morbidities. HBV patients enrolled will not have other co-morbid conditions which could increase their risk of adverse effects to ARO-HBV. The anticipated safety profile in NHVs and HBV patients is likely to be very similar. This is supported by Sponsor’s experience with ARC-521 Injection and ARC-520 Injection, which were siRNA therapeutics studied in single and multi-dose studies in NHV and CHB patient populations. Both ARC-521 Injection and ARC-520 Injection demonstrated a favorable safety profile in NHVs and HBV patients. Variation of dose frequency in the HBV patient cohorts (See Figure 1) is important to understand the dosing regimen that produces the deepest and most rapid reduction in viral antigen.

This study is similar to the ARC5211001 study which was executed successfully at the same site in New Zealand in NHVs and HBV patients.

The study is double-blind to limit the occurrence of conscious and unconscious bias in trial conduct and interpretation. Blinding will be achieved using a PBO product (0.9% normal saline). Inclusion of participants receiving PBO will reduce bias in the assessment of drug safety and tolerability. The study is randomized with a 2:1 (active:PBO) ratio to reduce bias.

Cohort 12 uses a combination of NUCs + ARO-HBV + JNJ-6379. Throughout the study all patients have been treated with the combination of NUCs + ARO-HBV. It is thought that by using an siRNA approach to silence production of viral antigen in combination with NUCs to inhibit viral replication and JNJ-6379 which inhibits capsid assembly and cccDNA formation the response to treatment and potentially the rate of functional cure could be enhanced. ARO-HBV + NUCs has been well tolerated throughout the AROHBV1001 study. JNJ-6379 in combination with NUCs has also been well tolerated in CHB clinical studies. In vitro, JNJ-6379 does not inhibit phosphorylation of tenofovir or entecavir. It is not expected that JNJ-6379 and ARO-HBV will have overlapping or additive toxicity. As such, the benefit of this combination “triple” therapy is expected to outweigh risk of toxicity.

6.3 *Criteria for Dose-escalation and Stopping Rules*

Escalation to the next cohort will proceed according to the study design until the 400 mg dose level and all subsequent cohorts are completed unless the trial is stopped early by the Data Safety Committee (DSC) or Sponsor. Dose escalation will require approval by the DSC based on all cumulative available safety data through Day 8 of the current cohort. Dose escalation will proceed until all cohorts are fully enrolled or until the study is stopped or the DSC votes to not escalate to the next dose.

A decision to stop the trial early or discontinue drug in an individual subject or group of subjects **may** (following a case-by-case decision based on consultation between the sponsor, DSC and the PI) be indicated based on any of the following:

1. A single Serious Adverse Event(SAE) (defined in Section 9.1) considered at least possibly related to ARO-HBV and/or JNJ-6379
2. One of the following abnormal results at least possibly related to ARO-HBV and/or JNJ-6379:
 - In NHVs, treatment emergent ALT or AST > 3X ULN which must be confirmed by repeat blood draw within 48 hours of initial results.
 - In CHB patients, treatment emergent ALT or AST > 3X Day 1 pre-dose baseline confirmed by repeat blood draw within 48 hours of initial results **AND** ALT > 10X ULN **AND** any one of the following:
 - Total Bilirubin newly elevated to 2X ULN AND 2X Day-1 pre-dose baseline (confirmed on repeat lab draw within 48 hours) or
 - Decrease in serum albumin of 0.5 g/dL or greater (confirmed on repeat lab draw within 48 hours)
 - Treatment emergent platelet count < 70,000 per microliter in NHVs or < 50,000 in CHB patients, confirmed on repeat measure within 48 hours of initial results
 - Treatment emergent serum creatinine > 180 µmol/L confirmed by repeat blood draw within 48 hours of initial results

Sponsor or PI can discontinue any subject at any time with or without DSC consultation. If such events (as described in #1, #2 above) occur and the subject is not discontinued from the study the reason for not discontinuing the subject will be included in DSC meeting minutes. Including, but not limited to the events listed above, the DSC may pause the study to additional dosing or dose escalation to provide time to evaluate safety data and recommend the action to be taken, which may include, but is not limited to one of the following:

- Discontinuation of a subject or group of subjects from the study
- The study is stopped immediately with no further dosing
- The study will continue until the current cohort is completed
- The study will continue, but the next dose escalation will be to a level midway between the current level and the next level specified in Section 8.3
- The study will continue as planned

If a serious adverse event (SAE) at least possibly related to study drug should occur for a single participant, subsequent dosing within that cohort **may** be put on hold pending a complete review of safety data by the DSC to determine if participant enrollment at the same dose may proceed, or if additional enrollment/dosing should stop. If following the DSC safety review it is deemed appropriate to restart dosing/enrollment, subject enrollment, dosing and dose escalation may proceed as planned.

6.4 *Duration of the Study*

For each NHV subject in the single dose cohorts, the duration of the study clinic visits is a maximum of 13 weeks from the beginning of the screening period to the Day 29 End-of-Study (EOS) examination.

For each CHB patient in the multi-dose cohorts the duration of the study clinic visits is approximately 25 weeks from screening to the Day 113 EOS examination. With the exception of Cohort 12 patients, all other CHB patients consenting to additional follow up will be followed as per Additional Follow-Up Schedule of Assessments (Table 1.5), every 56 days (± 5 days) for 5 additional visits after Day 113. Only Cohort 12 patients will require follow-up until the Day 337 (± 5 days) visit. Subjects consenting to additional follow up will continue on NUCs. Subjects not consenting to additional follow up will be followed per protocol based on Schedule of Assessment Tables 1.2, 1.3 and 1.4.

All CHB subjects who complete the study until Day 113 EOS examination are considered to complete the study and may continue to attend the Additional Follow-Up visits per the Schedule of Assessments (Table 1.5) if re-consent is obtained. If a subject withdraws from the Additional Follow-Up visits before the Day 337 (Cohort 12 only) or 393 visit, he or she will still be considered as a completed subject and reason for not continuing with the Additional Follow-Up visits per protocol will be recorded.

All CHB patients and NHV subjects will be contacted by phone 90 days after the EOS visit (Day 29 for NHVs and Day 113 for CHB patients) to confirm pregnancy status.

